9.5.3.3 ICP

Intracranial Pressure (ICP) will be collected for Days 1 – 6 of the study, at the investigators' discretion.

Descriptive summary statistics, categorical summaries (maximum daily ICP: 0 to <15, ≥15 to <25, ≥25 to <40 and ≥40 mmHg and maximum daily ICP: 0 to ≤20, >20 mmHg), and the number of subjects with maximum daily ICP ≥25 and maximum daily ICP >20 mmHg (cutpoints of particular interest) will be presented for the maximum ICP by treatment group and study day for the mITT population.

9.5.3.4 CPP

CPP is computed based upon simultaneously recorded ICP and blood pressure measurements, see Section 5 for formula. Summary statistics for the highest and lowest daily CPP values will be presented for each treatment group by Study Day.

CPP measurements in the following potentially clinically relevant categories will be presented for each treatment group: less than 50 mmHg, 50-<60 mmHg, 60-<70 mmHg and greater than or equal to 70 mmHg. The number and percentage of subjects within the various categories by Study Day will be summarized by treatment group.

Summary statistics will also be presented for the percentage of subjects with CPP measurements within the above specified categories at any time during treatment, where on-treatment will include all scheduled and unscheduled CPP measurements after the initiation of study medication.

9.5.3.5 TIL

TIL will be monitored during Study Days 1 – 6 (inclusive) while ICP is being monitored (i.e. up to 6 days).

Each of the unique treatments given on a study day used for ICP management will have a score of 1, and the maximum score (sum of the individual items) per assessment period (study day) is 10. It is assumed that there will be a stepwise progression of therapy (from sedation to surgical decompression). However, in the event that the most aggressive therapies are used, i.e. the subject has barbiturate administration or surgical decompression, this will result in a TIL score of 10 regardless of which of the other therapies have been administered.

The number of non-missing observations, absolute and relative frequency (n and percentage) of the subjects having at least one occurrence of the individual therapies (surgical decompression, barbiturate induced coma, hypothermia for ICP reduction, hyperventilation, pressor administration, hypertonic saline, mannitol, ventricular drainage, paralysis induction, and sedation) will be summarized for each treatment group. The most aggressive therapy received during Days 1-6, expressed as the highest stepwise level of the TIL, will also be summarized. Furthermore, the daily TIL score will be summarized as a continuous variable by Study Day and treatment group.

9.6 Safety Analyses

9.6.1 Adverse Events

For this study, it is intended to limit the collection of AEs to the window in which events are considered treatment-emergent. Treatment-emergent adverse events (TEAEs) are defined as events that start on or after the first dose of study medication and up to 15 days and 6 months after the initiation of study treatment, for AEs and SAEs respectively.

Partial start dates of AEs will be imputed in order to determine whether or not the AE is TE. If just the day is missing, and any date of dose administered is within the month of the AE, the AE will be treated as TE. If the month is missing and the year is present, and any date of dose administered is within the year of the AE, the AE will be treated as TE. If the year is missing,

the AE will be treated as TE. For the imputation, the day will be set to the first date of that month, or the first dose date, if the first dose date is within that month. Alternatively, if the month is missing the month will be set to January, or the first dose date, if the first dose date is within that year.

AEs will be coded using the MedDRA international thesaurus version 13.0 with no updates, adding system organ class (SOC) and preferred term. The AE summaries will be presented for TEAEs only. The total number of subjects reporting at least one AE and the number of AEs will be summarized by treatment group. The initial summary will also provide a breakdown of events that:

- Are treatment-related,
- Are serious,
- Are treatment-related and serious,
- Resulted in the study drug being prematurely discontinued,
- Are treatment-related and resulted in the study drug being prematurely discontinued,
- Resulted in death, and
- Are treatment-related and resulted in death.

Additionally, the overall summary of AEs will be summarized by treatment group for the subgroups of interest: gender, race group (white vs. non-white vs. not allowed to obtain), and age group (≤ 45 years vs. > 45 years).

The number and percentage of subjects with at least one TEAE and the number of TEAEs will be presented by SOC, preferred term, and treatment group for the following summaries:

- All AEs,
- All AEs by gender,
- All AEs by race group,
- All AEs by age group,
- Treatment-related AEs,
- All AEs, by maximum severity,
- Treatment-related AEs, by maximum severity,
- All AEs, by maximum relationship,
- All AEs that resulted in the study drug being prematurely discontinued, and
- Treatment-related AEs that resulted in the study drug being prematurely discontinued.

Additionally, the following AEs of special interest will be presented by treatment group: serious thromboembolic events such as thrombotic myocardial infarction, pulmonary embolism, deep vein thrombosis, ischemic stroke; allergic reactions; marked liver function abnormalities; serious infections such as pneumonia, sepsis, meningitis. Preferred terms for each AE of special interest will be identified by medical review prior to unblinding for the primary analysis. Preferred terms related to the following events will also be grouped to ensure similar events that are coded to different terms using MedDRA are summarized together: electrolyte imbalance, anemia, infusion site reactions, thrombocyte disorders, and seizures. These events will also be listed.

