9. ADVERSE EVENT COLLECTION AND REPORTING

9.1 Adverse Event Collection

All AEs will be recorded for the first 15 days after the start of administration of the study drug (5 days of drug infusion and 10 days post infusion). SAEs will be recorded for the entire 6-month period. The Adverse Events eCRF must be completed for all reported AEs and SAEs.

An adverse event is defined as: “Any untoward medical occurrence in a subject or clinical investigation subject administered a pharmaceutical product that does not necessarily have a causal relationship with this treatment.” An adverse event can therefore be any unfavorable and unintended sign (including an abnormal laboratory finding), symptom, or disease temporally associated with the use of a medicinal (investigational) product, whether or not related to the medicinal (investigational) product. This includes any newly occurring event or previous condition that has increased in severity or frequency since the administration of study drug. Instances of neuroworsening are considered AEs.

Details of any adverse or unexpected events, signs, and symptoms will be collected including details of onset, resolution, frequency, severity (as defined below), seriousness, relationship to the drug, effect on the study drug, treatments administered, and outcome. Any AE will be followed, whenever possible, until it returns to the baseline condition or becomes stable with no further change expected.

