The AE/SAE relationship to the study treatment will be judged as not related, possibly related, probably related, or related. It should be noted that the half-life of progesterone in BHR-100 was found to be 5.30 hrs (SD 0.66) in BHR's Phase 1 trial of healthy male subjects, with progesterone largely cleared by 24 hours.

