TIL will be monitored during Study Days 1 – 6 (inclusive). The administration of each of the following unique treatments will have a score of 1 and the maximum score (sum of the individual items) per assessment period (study day) is 10:

- Surgical decompression,
- Barbiturate induced coma,
- Hypothermia for ICP reduction,
- Hyperventilation ($\text{pCO}_2 < 30$),
- Pressor administration,
- Hypertonic saline,
- Mannitol,
- Ventricular drainage,
- Paralysis induction,
- Sedation.

Neuroworsening

Neuroworsening will be defined as the occurrence of any one of the following:

- A decrease in GCS motor score ≥ 2 ,
- Development of pupillary abnormalities,
- Any other neurological deterioration or progression of lesion on CT scan leading to a change in subject management.

Pupillary Response

Pupillary response will come from the assessment of right and left pupil reactivity as follows:

- If both right and left pupils react, pupillary response = bilateral,
- If only one of the right or left pupil reacts, pupillary response = unilateral, and
- If neither right nor left pupil reacts = no reactive pupils, or
- If the eyes are closed and reactivity is untestable = not testable.

Treatment-Emergent Adverse Events

Treatment-emergent adverse events (TEAEs) are defined as events that start on or after the first dose of study medication. For this study it is intended that AEs will be collected for 15 days

after the initiation of study treatment; serious adverse events (SAEs) will be collected from the time of infusion start throughout the course of the subject's participation in the study (6 months).

All AE tables will be presented for TEAEs only, listings will present all AEs (including those not deemed to be TE).

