Table 14.2.12.2 Summary of Individual TIL Therapies (mITT Population)

Therapy	BHR-100 (N=xx)	Placebo (N=xx)
Surgical Decompression	xx (xx.x %)	xx (xx.x %)
Barbiturate Induced Coma	xx (xx.x %)	xx (xx.x %)
Hypothermia	xx (xx.x %)	xx (xx.x %)
Hyperventilation (pCO ₂ <30)	xx (xx.x %)	xx (xx.x %)
Pressor Administration (to keep CPP>60)	xx (xx.x %)	xx (xx.x %)
Hypertonic Saline	xx (xx.x %)	xx (xx.x %)
Mannitol	xx (xx.x %)	xx (xx.x %)
Ventricular Drainage	xx (xx.x %)	xx (xx.x %)
Paralysis Induction	xx (xx.x %)	xx (xx.x %)
Sedation	xx (xx.x %)	xx (xx.x %)

Subjects may have received multiple therapies, and therefore may be counted in multiple rows.

Source: Listing 16.2.6.8.1.

Program: xxxxxxx.sas, Output: xxxxxxx.rtf, Generated on: DDMONYYYY xx:xx, Page x of x

Table 14.2.12.3 Summary of Maximum Therapy Intensity Level (mITT Population)

Therapy	Response	Statistic (N=xx)	BHR-100 (N=xx)	Placebo (N=xx)
Surgical Decompression			xx (xx.x %)	xx (xx.x %)
Barbiturate Induced Coma			xx (xx.x %)	xx (xx.x %)
Hypothermia			xx (xx.x %)	xx (xx.x %)
Hyperventilation (pCO ₂ <30)			xx (xx.x %)	xx (xx.x %)
Pressor Administration (to keep CPP>60)			xx (xx.x %)	xx (xx.x %)
Hypertonic Saline			xx (xx.x %)	xx (xx.x %)
Mannitol			xx (xx.x %)	xx (xx.x %)
Ventricular Drainage			xx (xx.x %)	xx (xx.x %)
Paralysis Induction			xx (xx.x %)	xx (xx.x %)
Sedation			xx (xx.x %)	xx (xx.x %)
No Intervention			xx (xx.x %)	xx (xx.x %)

Note: Subjects are summarized according to the maximum therapy received on Days 1-6.

Source: Listing 16.2.6.8.1.

Program: xxxxxxx.sas, Output: xxxxxxx.rtf, Generated on: DDMONYYYY xx:xx, Page x of x

Table 14.3.1.1 Overall Summary of Treatment Emergent Adverse Events (Safety Population)

Adverse Event Category	BHR-100 (N=xx)		Placebo (N=xx)	
	# (%) Subj	# AEs	# (%) Subj	# AEs
Any	xx (xx.x %)	xx	xx (xx.x %)	xx
Any Treatment-Related AE	xx (xx.x %)	xx	xx (xx.x %)	xx
Any Serious AE	xx (xx.x %)	xx	xx (xx.x %)	xx
Any Treatment-Related Serious AE	xx (xx.x %)	xx	xx (xx.x %)	xx
Any AE Leading to Premature Discontinuation of Study Drug	xx (xx.x %)	xx	xx (xx.x %)	xx
Any Treatment-Related AE Leading to Premature Discontinuation of Study Drug	xx (xx.x %)	xx	xx (xx.x %)	xx
Any AE Which Resulted in Death	xx (xx.x %)	xx	xx (xx.x %)	xx
Any Treatment-Related AE Which Resulted in Death	xx (xx.x %)	xx	xx (xx.x %)	xx

Note: Treatment-emergent adverse events are defined as events that start on or after the first dose of study medication.

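### Most treatment-emergent AE tables combine all AEs of Days 1–15 with serious events only from Day 16 to Month 6, under a definition that the SAP states in two ways

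*SAP*

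**What the plan says.** **Collection.** Protocol 9.1 sets two windows: "All AEs will be recorded for the first 15 days after the start of administration of the study drug" and "SAEs will be recorded for the entire 6-month period". The first is 5 days of infusion plus 10 days after it.

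**Definition.** SAP 9.6.1 carries both windows into the definition of a treatment-emergent AE (TEAE): events from the first dose "and up to 15 days and 6 months after the initiation of study treatment, for AEs and SAEs respectively". The footnote to Listing 16.2.7 repeats these limits. SAP Section 5 stops earlier: "Treatment-emergent adverse events (TEAEs) are defined as events that start on or after the first dose of study medication". The footnotes to the table shells in SAP Appendix 3 do the same: "Treatment-emergent adverse events are defined as events that start on or after the first dose of study medication".

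**Use.** Section 5 and 9.6.1 restrict the AE tables to TEAEs. The summaries listed in 9.6.1 include overall counts, system organ class and preferred term, sex, race and age groups, treatment-related events, "All AEs, by maximum severity" and maximum relationship. Percentages are of subjects per arm. No table in SAP Appendix 2 limits all AEs to Days 1–15, and none uses person-time.

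**Elsewhere.** SAP 9.6.3 gives SAEs their own tables (14.3.2.1 and 14.3.2.2). SAP 9.6.2 summarizes neuroworsening by Day 6 and by Day 15.

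**The concern.** After Day 15 an event can enter the pooled tables only if it is serious. A preferred-term percentage then adds 15 days of everything to about five and a half months of serious events. A reader cannot recover from the tables the AE incidence for the one period in which all AEs were collected.

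That period is also the one closest to exposure. The infusion lasts 120 hours, and Protocol 9.2 describes "progesterone largely cleared by 24 hours" in healthy volunteers. The severity and relationship tables are affected as well, because the late records are selected for seriousness.

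These tables carry the safety comparison. Protocol 8.5 says that AE occurrence and number of occurrences will be compared between arms, and Tables 14.3.1.1, 14.3.1.5, 14.3.1.9 and 14.3.1.15 are marked for the DSMB.

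The treatment may also change survival, and with it the time during which a late SAE can occur.

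**Working it through.** **1. Which tables mix windows**

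| Table or rows | Window |
|---|---|
| 14.3.1.1, any AE and any treatment-related AE | Mixed |
| 14.3.1.1, serious and fatal rows | One, to Month 6 |
| 14.3.1.2–14.3.1.4 (same rows by sex, race, age) | As 14.3.1.1 |
| 14.3.1.5–14.3.1.12 (SOC/PT, subgroup, related, severity, relationship) | Mixed |
| 14.3.1.13–14.3.1.14 (drug discontinuation) | In effect the 120-hour infusion |
| 14.3.1.15, serious thromboembolic events and serious infections | One, to Month 6 |
| 14.3.1.15, categories not limited to serious (allergic reactions, marked liver abnormalities) | Mixed |
| 14.3.1.16 | Subject listing, no percentages |
| 14.3.2.1–14.3.2.2 | One, to Month 6 |

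**2. Share of time.** The stated AE window reproduces: 5 + 10 = 15 days. All AEs are collected for 15/180 = 8.3% of planned days, and serious events only for 165/180 = 91.7%. Infusion plus 24 hours is 6/180 = 3.3%. These are shares of calendar time, not of events.

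**3. The two definitions.** Take a non-serious AE with onset on Day 18. Under Section 5 and the shells it is a TEAE and is counted. Under 9.6.1 and Listing 16.2.7 it is not. Such a record is possible: Protocol 6.5 allows the Day 15 visit, at which AEs are recorded, up to 5 days late unless ICU discharge comes first.

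**4. Survival**

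Inputs from Protocol 8.1: placebo vegetative/dead 29%, common odds ratio 1.5, 590 per arm. As a check on these inputs, Whitehead's formula N = 12(z₁₋α/₂ + z₁₋β)² / [ln(OR)²(1 − Σp̄³)] gives 1176 at α = 0.01 and 1180 at 0.0098, against the planned 1180.

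- BHR-100 odds of not vegetative/dead: (0.71/0.29) × 1.5 = 3.672, so the probability is 3.672/4.672 = 0.786. Vegetative/dead is 21.4%.
- Difference: 0.29 − 0.214 = 0.076, about 45 subjects per 590.

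Assumptions: all vegetative/dead are counted as dead, which overstates the mortality gap, and a late death contributes half of the 165 days.

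| Deaths by Day 15 | Late time at risk, BHR-100/placebo |
|---|---|
| All | 0.786/0.71 = 1.107 |
| Half | 1.073 |
| None | 1.044 |

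At an equal late hazard, BHR-100 would have 4–11% more non-fatal late SAEs. But fatal events are SAEs (Protocol 7.3.3 and 9.4). With all deaths early and a late-SAE incidence q in survivors, the patients with a fatal event or a late SAE are:

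- placebo: 0.29 + 0.71q
- BHR-100: 0.214 + 0.786q
- difference: −0.076(1 − q), which is −6.8 points at q = 0.1 and −4.6 points at q = 0.4.

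For event counts, let each death be one SAE and r be the non-fatal late SAEs per 165 survivor-days. The better-surviving arm has more events only if r exceeds 1 (all deaths early), 1.33 (half early) or 2 (none early). At r = 0.3 the net difference is −31 to −38 events.

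**5. Severity mix.** Assume 20% severe among early AEs, 80% severe among late SAEs, a early AEs per subject and r late SAEs per survivor, with 71% survivors. Pooled severe share = (0.2a + 0.8 × 0.71r)/(a + 0.71r).

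- a = 8, r = 0.1: 1.657/8.071 = 20.5%
- a = 3, r = 1: 1.168/3.71 = 31.5%

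**The case against.** **The tables are descriptive, and the data to look further exist.** The SAP plans no test or stopping threshold on them, and both arms share one ascertainment rule. SAEs have separate tables. Listing 16.2.7 gives onset date, study day, seriousness and treatment-emergent status for each event. This stands, and it limits the importance of the point. A listing does not replace a table for a reader of the report, however.

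**The conflict of definitions is narrow.** In Section 5 the sentence after the definition gives the two collection windows, and 9.6.1 says collection is meant to match the treatment-emergent window. Only a late non-serious AE is affected, and few are to be expected. That also stands, but the two rules still give different counts for such a record.

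**Stronger readings do not hold.** A reader might infer that every TEAE table is affected, or that the tables refer to no defined period. The table in the working shows several with one window, and both periods are defined; they differ by seriousness. A reader might also infer that the arm with more survivors will show more events. That holds for non-fatal late SAEs at an equal hazard. It does not hold for all events, because deaths are in the same numerator. The documents give neither the late SAE rate nor the timing of deaths, so the net direction is open.

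**Cutting every AE table at Day 15 would lose information.** Tables 14.3.2.1 and 14.3.2.2 show only SOC and preferred term. Late SAEs would leave their only planned severity, relationship and subgroup breakdowns, and the serious and fatal rows of 14.3.1.1 would no longer agree with the SAE tables. This is correct, and the fix has to allow for it.

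**Conclusion.** The point holds for most of the TEAE summary tables. Their incidence, severity mix and relationship mix refer to no single ascertainment period, and late counts depend on differential survival in an unknown direction. The definition needs one wording.

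The pooling and the conflict of definitions can be read from the SAP and need no assumption. How far they move any percentage cannot be computed, since the documents give no AE rates. For the same reason, dilution of an early safety signal is possible but not quantified. The 4–11% difference in late time at risk rests on the design odds ratio and on counting vegetative patients as dead. The severe share of 20.5–31.5% rests wholly on assumed rates.

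This is a cheap improvement to the interpretation of descriptive safety tables. The efficacy analysis, alpha and power are unaffected.

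**What to change.** 1. Use the 9.6.1 definition, with its 15-day and 6-month limits, in SAP Section 5 and in every shell footnote.
2. Present the all-AE SOC/PT, severity, relationship and subgroup tables, and the all-AE rows of 14.3.1.1–14.3.1.4, for onset through Day 15.
3. Keep the serious and fatal rows of 14.3.1.1, and Tables 14.3.2.1–14.3.2.2, through Month 6. Label the period and give the number of patients at risk after Day 15. Treat the serious and fatal rows of 14.3.1.2–14.3.1.4 in the same way.
4. Add severity and relationship breakdowns for SAEs through Month 6, so that no late event drops out. If SAEs are wanted by SOC/PT within sex, race and age groups, add those too.
5. In 14.3.1.15, show the categories not limited to serious events in two parts: onset to Day 15 (all), and Day 16 to Month 6 (serious only).

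The cost is SAP wording, an onset-date filter and a few extra descriptive tables. No new data are needed.

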9.6.2 Neuroworsening

See Section 5 for definition of neuroworsening. The incidence of any episode of neuroworsening occurring \leq Day 6 and \leq Day 15 will be summarized.

Details of all neuroworsening events will also be listed.

9.6.3 Deaths and Serious Adverse Events

The number and percentage of subjects with at least one SAE and the number of events will be presented by SOC, preferred term and treatment group for the following summaries:

- All SAEs, and
- Treatment-related SAEs.

The primary cause of death as recorded on the death report will be summarized by treatment group and overall for the mITT population.

9.6.4 Laboratory Data

Laboratory data (coagulation, hematology, serum chemistry and urinalysis) will be collected at baseline, end of study treatment (Day 6), and Day 15 of the study.

The status of clinically significant (non AE) abnormalities (resolved, ongoing, or lost to follow-up) will be summarized for Day 15 by laboratory parameter and treatment group in the safety population.

Clinically significant (non-AE) abnormal lab results (coagulation, hematology, serum chemistry, and urinalysis) will be listed.

Coagulation, hematology, and serum chemistry laboratory assessments will also be summarized descriptively for baseline, Day 6, and Day 15. The change from baseline will be summarized for Day 6 and Day 15. All lab parameters will be summarized in standard SI units.

All lab results from Baseline, Day 6, and Day 15 will be listed.

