7.2.1 Adverse Events and Serious Adverse Events

Adverse events whether reported, observed, or elicited by indirect questioning will be captured from the time of infusion start through 10 days post-infusion (Days 1-15). SAEs will be captured from the time of infusion start throughout the course of the subject's participation in the study (6 months). The AE/SAE relationship to the study treatment will be judged as not related, possibly related, probably related, or related. Ongoing AEs will be followed to resolution, whenever possible.

Particular attention should be paid to the following potential risks previously identified as associated with administration of progesterone: serious thromboembolic events such as thrombotic myocardial infarction, pulmonary embolism, deep vein thrombosis, ischemic stroke; allergic reactions; marked liver function abnormalities; serious infections such as pneumonia, sepsis, meningitis.

All SAEs will be reported by telephone or written report within 24 hours of being notified of the event to the Sponsor's Medical Monitor and then reported to each site's IRB/IEC according to the local regulations. Serious adverse events that persist at Month 6 post-injury will be documented as to their final status.

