7.2.3 Laboratory Safety Tests

Standard clinical safety labs will be measured locally at the sites and recorded for the specified time points (see [Appendix B](#) for details). The Investigator will assess all abnormal lab values at these time points for clinical significance; if categorized as adverse events, they will be collected and recorded similarly to other AEs. All clinically significant abnormal lab values will be followed until resolution, whether or not they are deemed AEs by the investigator. If resolution is not seen, a justification as to the cause for such an abnormality, such as if due to an underlying pre-existing condition, associated co-morbidity, etc, will be recorded.

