8.5 Adverse Event Safety Data

Data on adverse events will be presented descriptively, grouping events by body system. Results will be presented for all adverse events, including instances of neuorworsening and abnormal clinically significant laboratory findings deemed as AEs by the Investigator.

The occurrence of adverse events will be compared between treatment groups, including the proportion of subjects in each arm suffering at least one episode of the event as well as the comparison of the distribution of the number of occurrences of the event. Additional presentations of AE data may be requested by the Data and Safety Monitoring Board (DSMB) (see Section 10.4).

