Table 14.3.1.8	Treatment Emergent Adverse Events by System Organ Class, Preferred Term, and Age Group (Safety Population)		
Table 14.3.1.9	Treatment-Related Treatment Emergent Adverse Events by System Organ Class and Preferred Term (Safety Population)	14.3.1.5	X
Table 14.3.1.10	Treatment Emergent Adverse Events by Maximum Severity, System Organ Class and Preferred Term (Safety Population)		
Table 14.3.1.11	Treatment-Related Treatment Emergent Adverse Events by Maximum Severity, System Organ Class and Preferred Term (Safety Population)	14.3.1.9	
Table 14.3.1.12	Treatment Emergent Adverse Events by Maximum Relationship, System Organ Class and Preferred Term (Safety Population)		
Table 14.3.1.13	Treatment Emergent Adverse Events Leading to Premature Discontinuation of Study Drug by System Organ Class and Preferred Term (Safety Population)	14.3.1.5	
Table 14.3.1.14	Treatment-Related Treatment Emergent Adverse Events Leading to Premature Discontinuation of Study Drug by System Organ Class and Preferred Term (Safety Population)	14.3.1.5	
Table 14.3.1.15	Treatment Emergent Adverse Events of Special Interest (Safety Population)		X
Table 14.3.1.16	List of Adverse Events of Special Interest (Safety Population)		X
Table 14.3.2.1	Serious Adverse Events by System Organ Class and Preferred Term (Safety Population)	14.3.1.5	X
Table 14.3.2.2	Treatment-Related Serious Adverse Events by System Organ Class and Preferred Term (Safety Population)	14.3.1.5	X
Table 14.3.2.3	Primary Cause of Death (mITT Population)		X
Table 14.3.4.1	Post-Baseline Abnormal, Clinically Significant (non-AE) Laboratory Test Results: Coagulation (Safety Population)		X
Table 14.3.4.2	Post-Baseline Abnormal, Clinically Significant (non-AE) Laboratory Test Results: Hematology (Safety Population)	14.3.4.1	X
Table 14.3.4.3	Post-Baseline Abnormal, Clinically Significant (non-AE) Laboratory Test Results: Serum Chemistry (Safety Population)	14.3.4.1	

Output	Title	Use Table Shell	DSMB*
Table 14.3.4.4	Post-Baseline Abnormal, Clinically Significant (non-AE) Laboratory Test Results: Urinalysis (Safety Population)		
Table 14.3.4.5	List of Post-Baseline Abnormal, Clinically Significant (non-AE) Laboratory Test Results: Coagulation (Safety Population)	14.3.4.9	X
Table 14.3.4.6	List of Post-Baseline Abnormal, Clinically Significant (non-AE) Laboratory Test Results: Hematology (Safety Population)		X

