Preferred Term 3	xx (xx.x %)	xx (xx.x %)	xx (xx.x %)	xx (xx.x %)	xx (xx.x %)	xx (xx.x %)	xx (xx.x %)	xx (xx.x %)
Preferred Term 4	xx (xx.x %)	xx (xx.x %)	xx (xx.x %)	xx (xx.x %)	xx (xx.x %)	xx (xx.x %)	xx (xx.x %)	xx (xx.x %)
Preferred Term 5	xx (xx.x %)	xx (xx.x %)	xx (xx.x %)	xx (xx.x %)	xx (xx.x %)	xx (xx.x %)	xx (xx.x %)	xx (xx.x %)

Note: Treatment-Emergent adverse events are defined as events that start on or after the first dose of study medication.

Note: Adverse Events are coded by MedDRA Version 13.0.

Note: For each system organ class and preferred term, subjects are included only once, even if they experienced multiple events in that system organ class or preferred term.

Note: Percentages are based on the number of subjects in each treatment group in the population of interest.

Note: If the relationship of an Adverse Event is missing, then it is considered to be related to study medication.

Source: Listing 16.2.7.

Program: xxxxxxx.sas, Output: xxxxxxx.rtf, Generated on: DDMONYYYY xx:xx, Page x of x

[Note to Programmer: Each subject is counted only once in the particular AE class, under the most related category they experienced for that class of AE. If the AE relationship to study medication is missing, then it is considered to be related.]

Table 14.3.1.13 Treatment Emergent Adverse Events Leading to Premature Discontinuation of Study Drug by System Organ Class and Preferred Term (Safety Population)

Table 14.3.1.14 Treatment-Related Treatment Emergent Adverse Events Leading to Premature Discontinuation of Study Drug by System Organ Class and Preferred Term (Safety Population)

[Use shell for Table 14.3.1.7, change footnotes accordingly.]

Table 14.3.1.15 Treatment Emergent Adverse Events of Special Interest (Safety Population)

AE of Special Interest Preferred Term	BHR-100 (N=xx)		Placebo (N=xx)	
	# (%) Subj	# AEs	# (%) Subj	# AEs
Any Adverse Event of Special Interest	xx (xx.x %)	xx	xx (xx.x %)	xx
Serious Thromboembolic Events	xx (xx.x %)	xx	xx (xx.x %)	xx
Preferred Term 1	xx (xx.x %)	xx	xx (xx.x %)	xx
Preferred Term 2	xx (xx.x %)	xx	xx (xx.x %)	xx
...				
Thrombotic Myocardial Infarction	xx (xx.x %)	xx	xx (xx.x %)	xx
Pulmonary Embolism	xx (xx.x %)	xx	xx (xx.x %)	xx
Deep Vein Thrombosis	xx (xx.x %)	xx	xx (xx.x %)	xx
Ischemic Stroke	xx (xx.x %)	xx	xx (xx.x %)	xx
Allergic Reactions	xx (xx.x %)	xx	xx (xx.x %)	xx
Marked Liver Function Abnormalities	xx (xx.x %)	xx	xx (xx.x %)	xx
Serious Infections	xx (xx.x %)	xx	xx (xx.x %)	xx

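### Marked liver abnormality is a pre-named risk, yet no planned output counts affected subjects by arm on an objective laboratory criterion, and the adverse event tables carry no between-arm estimate

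*SAP*

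**What the plan says.** **The risk.** Protocol 7.2.1 asks for particular attention to a list of potential progesterone risks that includes "allergic reactions; marked liver function abnormalities". Neither document says how large a rise must be to count as marked.

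**From laboratory value to event.** Protocol 7.2.3 leaves the judgement to the site: "The Investigator will assess all abnormal lab values at these time points for clinical significance". Under Protocol 9.2 a significant change may, but need not, be recorded as an AE. If a broader diagnosis explains the value, only the diagnosis is reported.

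**What the SAP tabulates.**
- AEs of special interest are found through coded terms (SAP 9.6.1): "Preferred terms for each AE of special interest will be identified by medical review prior to unblinding for the primary analysis". Table 14.3.1.15 has a liver row with subjects (%) and number of events by arm.
- SAP 9.6.4 says of laboratory results: "The status of clinically significant (non AE) abnormalities (resolved, ongoing, or lost to follow-up) will be summarized for Day 15", by parameter and arm. Table 14.3.4.3 does this for AST, ALT, alkaline phosphatase (ALP) and GGT. Its shell counts results and leaves out those classed as AEs.
- Table 14.3.4.11 summarises all enzyme values and changes, including minimum and maximum. The listings carry each scheduled value with its reference range and AE status.

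**AE comparison.** Protocol 8.5 says: "The occurrence of adverse events will be compared between treatment groups, including the proportion of subjects in each arm suffering at least one episode" and adds a comparison of the distribution of the number of occurrences. It opens by calling the presentation descriptive, and it names no test or effect measure.

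**The concern.** In severe trauma an enzyme rise has many possible explanations, so whether it becomes an AE, a flagged non-AE result or neither depends on the site. A large rise that the investigator thinks unimportant reaches neither Table 14.3.1.15 nor Table 14.3.4.3. It survives only in the listing and in the continuous summary, where one maximum per arm does not show how many subjects had such a rise.

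The conclusion on a named risk would then rest on labelling, with no objective count to check it against. Without an interval, a reader also cannot tell what excess the trial rules out. The SAP already uses better tools elsewhere: it counts subjects by cut-point for the exploratory intracranial pressure (ICP) and cerebral perfusion pressure (CPP) variables (SAP 9.5.3.3 and 9.5.3.4), and it gives mortality a difference with a 95% interval (SAP 9.5.2.1).

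**Working it through.** **1. Where a liver abnormality can appear**

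| Investigator's label | By-arm count | Unit | To DSMB? |
|---|---|---|---|
| AE | Table 14.3.1.15 and the general AE tables | subjects and events | yes (14.3.1.15, 14.3.1.16, 14.3.1.5) |
| Significant, not an AE | Table 14.3.4.3 | results | no; the by-subject list 14.3.4.7 is sent |
| Not significant | none | – | no |

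No row or table adds these together. The matching coagulation and haematology tables (14.3.4.1 and 14.3.4.2) are marked for the DSMB; 14.3.4.3 is not. Neither the chemistry summary 14.3.4.11 nor the full chemistry listing is marked.

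**2. AE comparison.** SAP 9.6.1 and its shells give subjects (%) and event totals by arm. No AE table has a difference, ratio or interval, and none shows the number of episodes per subject. SAP 1.1 lists two changes from the protocol; this is not one of them.

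**3. The denominator.** The plan states no figure for liver events, so the only planned figure to reproduce is the sample size. Whitehead's formula gives n per arm = 6(z₀.₉₉₅ + z₀.₉₀)² / [(ln 1.5)² (1 − Σp̄ᵢ³)]. With placebo proportions 31/21/19/29% and an odds ratio of 1.5, 1 − Σp̄ᵢ³ = 0.923, and n = 6(2.576 + 1.282)² / (0.1644 × 0.923) ≈ 588. The stated 590 per arm therefore holds, and SAP 3.1 defines it as subjects receiving study drug, so it serves as the safety denominator.

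**4. Precision an interval would give.** The documents give no liver event rate; assume equal rates p in both arms. Half-width = 1.96 × √[2p(1 − p)/590].
- p = 2%: 1.96 × √(0.0392/590) = 1.6 points
- p = 5%: 1.96 × √(0.095/590) = 2.5 points
- p = 10%: 1.96 × √(0.18/590) = 3.4 points

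**5. What incomplete capture would do.** Assume true rates of 5% on placebo and 10% on BHR-100, with the same capture share in both arms. SE of the difference = √[p₁(1 − p₁)/590 + p₂(1 − p₂)/590]; SE of the log ratio = √[(1 − p₁)/(590p₁) + (1 − p₂)/(590p₂)].

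| Capture | Expected subjects | Difference, points (95% CI) | Ratio (95% CI) |
|---|---|---|---|
| 100% | 29.5 vs 59 | 5.0 (2.0 to 8.0) | 2.0 (1.30 to 3.07) |
| 50% | 14.8 vs 29.5 | 2.5 (0.3 to 4.7) | 2.0 (1.08 to 3.70) |
| 25% | 7.4 vs 14.8 | 1.3 (−0.3 to 2.8) | 2.0 (0.83 to 4.81) |

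The ratio is preserved and its interval widens. The absolute difference falls in proportion to capture, faster than its own interval narrows.

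**The case against.** Much is already planned, and four stronger readings that a reader might infer fail.

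- *Liver abnormality is never counted from laboratory values.* Table 14.3.4.3 counts flagged enzyme results by arm and visit. With one scheduled sample at Day 6 and one at Day 15, a count within one enzyme and visit is close to a count of subjects. It still cannot be added across enzymes or visits, and it omits AE-classed and unflagged rises.
- *The signal is under-counted.* Nothing shows this. Protocol 7.2.3 requires every abnormal value to be assessed and significant ones to be followed, AE or not. A flagged non-AE case is not lost; it sits in another table. The capture shares above are assumptions.
- *The AE comparison has been dropped.* Protocol 8.5 calls the presentation descriptive, the synopsis speaks of counts, and side-by-side proportions meet the first half of the statement. A risk difference is an improvement, not a broken commitment. Only the distribution of occurrences has no output at all.
- *The DSMB cannot see liver results.* It receives Table 14.3.4.7, which gives subject, arm, value and range, and the special-interest tables. Under the synopsis it decides what data and comparisons it needs.

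A further fair point is that counting every high post-baseline value would include rises already present at screening. The fix below meets it.

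**Conclusion.** The concern holds in limited form. A pre-named risk has no numeric definition and no by-arm count of affected subjects that is independent of investigator labelling. The AE and non-AE sources are kept apart, and the DSMB is not sent the by-arm chemistry table. The comparison of the number of occurrences in Protocol 8.5 has no SAP output and is not declared as a change.

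The effect on the conclusions cannot be sized from the documents. The half-widths of 1.6 to 3.4 points assume equal rates of 2% to 10% and a full 590 per arm. Deaths or missing samples before Day 6 or Day 15 would widen them. The capture example also assumes equal capture in both arms; under blinding that is plausible but not guaranteed. This is a worthwhile, nearly free improvement. Primary efficacy is not affected.

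**What to change.** Before unblinding:

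1. Add a by-arm table of subjects whose highest post-baseline ALT, AST, ALP or GGT exceeds stated multiples of the local upper limit, whatever the AE status. The documents give no multiples, so they must be written into the SAP before unblinding. Show the result against baseline category, as a shift, so that rises present at screening are not counted as new. Use subjects with at least one post-baseline value as the denominator. Bilirubin is not in Protocol Appendix B, so a combined enzyme and bilirubin criterion cannot be derived.
2. Mark this table and Table 14.3.4.3 for the DSMB.
3. Add a risk difference with 95% CI to the special-interest rows of Table 14.3.1.15.
4. Tabulate the number of episodes per subject by arm, or record the omission in SAP 1.1.

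The cost is programming from values and reference ranges already collected, and a little more safety output. The intervals would not be adjusted for multiplicity and should be labelled descriptive. With two scheduled post-baseline samples, a short-lived peak between them could still be missed.
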